Duloxetine. We chose duloxetine as the first line drug because: (1) it has established efficacy for CMP and Food and Drug Administration (FDA) approval for that indication; and (2) it is available in generic form, which makes it more readily available. At study entry, all participants will receive duloxetine 30 mg once daily for one week; subjects who are able to tolerate 30 mg and do not have chronic kidney disease III (CKD-3) will increase to 60 mg once daily for 24 weeks. At week 25, participants will return to the research clinic for outcome assessments. At the last study visit (week 25), participants who would like to stop the medication, will be provided duloxetine 30 mg once daily for 7 days and medication treatment will then stop (tapering regimen). Subjects already taking 30 mg daily will stop dosing at their week 25 visit. Those who would like to continue duloxetine will be prescribed a 2-week supply of duloxetine and will be instructed to talk to their primary care provider (PCP). In addition, the investigator will send a Wake One message to the PCP to consider continuation of duloxetine.

Other treatments. The use of over-the-counter analgesic medications will be permitted and assessed to adjust for co-intervention differences between groups in the analyses.

For further details, see Section 6, Study Interventions or Experimental Manipulations.

Study Duration^{*}:

[figure not shown]
The estimated time from when the study opens to enrollment until completion of data collection is 45 months.

Participant Duration:

The time it will take for each individual participant to complete all study-related tasks is 25 weeks.

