1.3 SCHEDULE OF ACTIVITIES

Table 1. Study Measures and Time Points for Data Collection in PRECICE

Telephone Contacts/Visits ^a	Pre-Screening Visit	Week 0	Week 1	Week 2	Week 3	Week 4	Week 6	Week 10	Week 13	Week 14	Week 18	Week 22	Week 25	PRN
Type of Contact/Visit ^{b,c}	TC	IPV	IPV	TC	TC	TC	TC	TC	IPV	TC	TC	TC	IPV	PRN
Screening														
Phone Pre-Screening	✓													
Randomization			✓											
Physical Measures														
Blood Pressure	✓	✓							✓				✓	
Height	✓												✓	
Weight	✓												✓	
Urine Pregnancy Test	✓								✓					
Questionnaires														
3-item Pain Intensity Interview	✓								✓				✓	
Compiled Questionnaires		✓							✓				✓	
o Brief Pain Inventory														
o Generalized Anxiety Disorder (GAD-7)														
o Patient Health Questionnaire (PHQ8)														
o Global Rating of Change (GRoC)														
o Pain Catastrophizing Scale (PCS)														
o PROMIS Adult Self-Report														
o Chronic Pain Coping Inventory (CPCI)														
Demographics with Medical Diagnosis		✓												
Informed Consent		✓												
Missed Visit Form													✓	
Modified Pain Detect	✓													
Non-study Medication List	✓								✓				✓	
Nurse Counselling Tracking Form						✓		✓	✓		✓	✓	✓	
Opioid Risk Tool	✓													
Participant Status													✓	
Serious Adverse Event Report Form													✓	
Study Drug Accountability Log	✓ ^d	✓ ^e								✓			✓ ^f	
Study Medication Modification				✓						✓			✓ ^g	
Study Medication Symptom Monitoring Form		✓ ^h	✓ ⁱ			✓ ⁱ			✓ ⁱ		✓		✓ ^j	
TAPS – Tobacco, Alcohol, Prescription	✓												✓	
EMR Health Care Utilization ^h														

^a Weeks with participant contact are listed on this table.

^b IPV indicates in-person visit.

^c TC indicates telephone contact.

^d At study entry, all participants will receive duloxetine 30 mg once daily for one week.

^e At week 1, participants will receive duloxetine 60 mg once daily for 24 weeks.

^f At week 25, all participants will be provided duloxetine 30 mg once daily for 7 days and medication treatment will then stop (tapering regimen).

^g Phone administration on as needed basis only if participant calls the research office and complains of a potential side effect.

^h EMR Health Care Utilization will be collected at one year after randomization.

ⁱ Option of using text messaging as an adjunct to phone calls to assess duloxetine symptoms monitoring at weeks 2 and 4.

Revised 07/19/2021

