5.2 EXCLUSION CRITERIA

An individual who meets any of the following criteria will be excluded from participation in this study:

1. uncontrolled hypertension - sitting systolic blood pressure >170 mmHg or diastolic blood pressure >100 mmHg at screening - (because duloxetine rarely increases blood pressure);
2. active suicidal ideation;
3. planned elective surgery during the study period (to avoid the confounding effect of possible complicated post-surgery recovery course on the primary outcome);
4. ongoing unresolved disability claims;
5. inflammatory arthritis (e.g., lupus and ankylosing spondylitis);
6. cancer-related musculoskeletal pain;
7. pregnancy;
8. history of bipolar disorder or schizophrenia;
9. narrow angle glaucoma;
10. participant reported chronic kidney disease stage 4, eGFR <30 and/or severe renal impairment (creatinine clearance <30);
11. current use of duloxetine;
12. current use of any of the following medications (to avoid adverse drug-to-drug interactions): tricyclic antidepressant > 25 mg daily dose, monoamine oxidase inhibitors, fluoxetine, sertraline, paroxetine, citalopram, escitalopram, venlafaxine, milnacipran, mirtazapine, , or aripiprazole, serotonin precursors (e.g., tryptophan), and strong CYP1A2 inhibitors (e.g., ciprofloxacin, other fluoroquinolones, fluvoxamine and verapamil);
13. poly-pharmacy (defined as concurrent daily use of 4 or more centrally acting medications for anxiety (anxiolytics), insomnia (hypnotics), anti-psychotic and anticonvulsants (gabapentin and pregabalin are permitted, if subject on a stable dose for at least 4 weeks).

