2. Second phase: This phase is devoted to strategies that strengthen commitment to practice newly learned pain coping skills regularly and consistently. Specifically, the third call would include helping the patient develop a plan for change (i.e. shift from why the patient should consider change to how the patient will make changes) communicating free choice, and reviewing consequences of adaptive vs. maladaptive pain-related behaviors. The fourth phone call would involve asking for a commitment to practice new skills and a plan worksheet.
3. Third phase: The last 2 calls are for follow-through strategies to prevent relapse. To review the changes that have occurred since the last session, the MI-trained health care professional will praise and reinforce any and all approximations of progress. He or she will also review behavioral indicators of motivation, patient's responses to questions concerning reasons for making or maintaining changes, and barriers to adherence. He or she will again obtain a commitment to follow through on the new plan.

Duloxetine. We chose duloxetine as the first line drug because: (1) it has established efficacy for CMP and FDA approval for that indication; and (2) it is available in generic form, which makes it more readily available.

At study entry, all participants will receive duloxetine 30 mg once daily for one week. At Week 1, subjects who tolerate the 30 mg daily dose and do not have chronic kidney disease stage 3 will begin 60 mg once daily for 24 weeks. Subjects with CKD-3 tolerating 30mg daily, will continue on 30mg for 24 weeks. At week 25, participants will return to the research clinic for outcome assessments.

To assure safety of study participants, subjects will complete a symptom monitoring form (formerly labeled as medication side effects checklist) at week 1, week 2, week 4, week 13 and week 25. The subject may be contacted via text messaging as an adjunct to phone calls to assess duloxetine symptoms

monitoring at weeks 2 and 4 and for appointment reminders. The medical safety officer will be informed of any AEs (at week 1, week 2, week 4, week 13 and week 25) that require medical attention. For AEs that require medical attention, the study Medical Safety Officer will directly contact the participant to provide immediate care and guidance.

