At the last study visit (week 25), participants who would like to stop the medication will be provided duloxetine 30 mg once daily for 7 days and medication treatment will then stop (tapering regimen). Subjects already taking 30 mg daily will stop dosing at their week 25 visit. Those who would like to continue duloxetine will be prescribed a 2-week supply of duloxetine and will be instructed to talk to their primary care provider (PCP). In addition, the investigator will send a Wake One message to the PCP to consider continuation of duloxetine.

Other treatments. The use of over-the-counter analgesic medications will be permitted and assessed to adjust for co-intervention differences between groups in the analyses.

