6.1.2 ADMINISTRATION AND/OR DOSING

See Duloxetine dosing information under Section 6.1.1.

See MOP chapter 09, Intervention, for more details.

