7	03/28/2022	Changed “coach” to “health care professional” throughout the protocol and updated the analysis plan text regarding painful body sites stratification.	Changed “coach” to reflect a more generic term. The health care professionals trained in MI may range from a coach to PhD level. Updated the analysis plan based on decisions we made about the painful body sites stratification.
8	11/01/2022	Updated description of site enrollment facilities to add providers outside of the Atrium Health system	Enhance recruitment
		5.2 Eligibility criteria: revised to add inclusion of CKD-3 patients	Enhance recruitment
		5.2 Eligibility criteria: clarified criteria for uncontrolled hypertension	Safety
		5.2 Eligibility criteria: clarified use of gabapentin and pregabalin	Safety
		6.1.1 Revised to include drug dosing for subjects with CKD -3; text messaging may be used to contact subjects; clarified end of study drug discontinuation procedure	Safety
		10.1.7 Revised to reflect data collection oversight process	Clarification
		Editorial revisions and administrative changes throughout	Clarification

REFERENCES

7. Staud R. Abnormal endogenous pain modulation is a shared characteristic of many chronic pain conditions. *Expert Rev Neurother.* 2012;12(5):577-585.

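### Table 1 footnote e gives 60 mg duloxetine from Week 1 with no exception, but Section 6.1.1 keeps participants with CKD-3 on 30 mg; footnote f also misstates drug supply at Week 25

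*Combined protocol and SAP*

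**What the plan says.** **Week 1 dose.** Table 1 footnote e (Section 1.3) states: "At week 1, participants will receive duloxetine 60 mg once daily for 24 weeks". The Synopsis (Section 1.1) is conditional: "subjects who are able to tolerate 30 mg and do not have chronic kidney disease III (CKD-3) will increase to 60 mg once daily". Section 6.1.1 repeats both conditions and adds the rule for the excepted group: "Subjects with CKD-3 tolerating 30mg daily, will continue on 30mg for 24 weeks".

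**Which section governs.** Section 6.1.2, on administration and dosing, contains no dose of its own. It says "See Duloxetine dosing information under Section 6.1.1" and then refers to the Manual of Procedures (MOP) for more detail.

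**Who can enrol.** Exclusion 10 in Section 5.2 covers "participant reported chronic kidney disease stage 4, eGFR <30 and/or severe renal impairment", so a patient with CKD-3 is eligible.

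**Week 25 supply.** Footnote f states: "At week 25, all participants will be provided duloxetine 30 mg once daily for 7 days and medication treatment will then stop (tapering regimen". Sections 1.1 and 6.1.1 instead give three routes:

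- a 7-day taper for those who want to stop;
- no taper for those on the lower dose: "Subjects already taking 30 mg daily will stop dosing at their week 25 visit";
- a two-week supply, with a message to the primary care provider, for those who want to continue.

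**The concern.** Two parts of the current protocol give different doses to the same participants. Section 8.1 sends readers to the Schedule of Activities for the timing of procedures at each visit, and footnotes e and f are attached to the Study Drug Accountability Log row. Staff working from the table at the Week 1 visit would find 60 mg and nothing to tell them that a participant with CKD-3 should stay on 30 mg.

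What is at stake is dosing in a renally impaired subgroup. Table 1 lists no kidney function test, and Section 2.3.1 says the study adds no tests, so no scheduled laboratory result would reveal the error. Symptom monitoring would act only after exposure.

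Footnote e also omits the condition that 30 mg be tolerated. This adds little risk, because Sections 2.3.1 and 8.2 already provide for reducing or stopping the drug when it is not tolerated.

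**Working it through.** The plan states no statistical figure here. The check is a comparison of texts, followed by simple dose arithmetic.

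**Step 1. Compare the rules.**

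| Participant | Table 1 footnote | Sections 1.1 and 6.1.1 |
|---|---|---|
| Week 1, tolerates 30 mg, no CKD-3 | 60 mg/day | 60 mg/day |
| Week 1, tolerates 30 mg, CKD-3 | 60 mg/day | 30 mg/day |
| Week 25, on 60 mg, wants to stop | 30 mg for 7 days, then stop | Same |
| Week 25, already on 30 mg | 30 mg for 7 days, then stop | Stop at the visit |
| Week 25, wants to continue | 30 mg for 7 days, then stop | Two-week supply and hand-off to primary care |

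Section 1.1 only implies the 30 mg dose in CKD-3, by leaving that group out of the increase. Section 6.1.1 states it outright. The two sections agree, and the footnotes are what differ.

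**Step 2. Size of the Week 1 difference, per participant with CKD-3.**

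- Days: 24 × 7 = 168.
- Text: 30 mg × 168 = 5,040 mg.
- Footnote e: 60 mg × 168 = 10,080 mg.
- Ratio: 10,080 / 5,040 = 2.

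These totals assume the wrong dose runs for the full 24 weeks.

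**Step 3. Size of the Week 25 difference.**

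- Already on 30 mg: footnote f supplies 7 × 30 mg = 210 mg; the text supplies none.
- Wanting to continue: footnote f supplies 7 days and then stops; the text supplies 14 days, a difference of 14 − 7 = 7 days, plus the hand-off.

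**Step 4. How many participants.** The documents give no CKD-3 count. With an assumed share of 1% to 5% of the 280 planned: 280 × 0.01 = 2.8 and 280 × 0.05 = 14.0, so about 3 to 14. At any assumed share this is too high, because those enrolled before CKD-3 became eligible do not count.

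**Step 5. How the mismatch arose.** The amendment history (Section 10.4) is used here only for dates; both sides of the conflict are current text. Version 8 (11/01/2022) admitted patients with CKD-3 and records "6.1.1 Revised to include drug dosing for subjects with CKD -3". Table 1 still carries a revision date of 07/19/2021, so footnote e was not carried forward. Footnote f has a different history: the option to continue duloxetine came in with version 4 (01/14/2021), before the table's own revision date, so version 8 does not explain that omission.

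**The case against.** The best defence is that the dosing rule is not in doubt. The restriction appears in the Synopsis and in Section 6.1.1, and Section 6.1.2 directs readers to 6.1.1. Table 1 is titled as a schedule of measures and data collection times, and its footnotes mark a form row. Footnote e says participants, not all participants, so the lack of an exception is silence rather than a statement. Staff may in practice dose from the MOP, which is not available for review. The amendment history gives safety as the reason for a row that also covers text messaging and end-of-study discontinuation, so that label cannot be pinned to CKD-3 dosing alone; the reason given for admitting these patients is recruitment. The protocol describes no specific harm from 60 mg in CKD-3. The number affected is unknown and could be close to zero.

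Much of this stands. A careful reader can resolve the conflict, no misdosing is shown, the head count is only an assumption, and footnote f concerns only drug supplied after the final assessment. None of it removes the contradiction. Footnote e states a dose, a frequency and a duration, and the sponsor has treated it as operative before: it was amended on 04/19/2021 to correct its dose wording. The unseen MOP might limit the practical effect, but it does not make the protocol consistent.

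**Conclusion.** The concern holds. Footnote e is wrong as written for participants with CKD-3: it gives 60 mg/day where Section 6.1.1 gives 30 mg/day, a two-fold difference. Footnote f is wrong for participants already on 30 mg and for those who wish to continue, with smaller consequences. The Week 1 finding rests on the literal reading of the footnote and on CKD-3 being eligible, and the current text supports both. The range of 3 to 14 participants rests on an assumed share with no source in the protocol and is an overstatement.

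There is no demonstrated effect on the trial's inference. All three arms receive duloxetine under the same footnotes, the primary analysis follows randomized assignment regardless of adherence (Section 9.4.2), and the sample size calculation does not depend on the dosing rule. This is a dosing safety and consistency correction that should be made, not a threat to the primary comparison.

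**What to change.** Treat Section 6.1.1 as the source and amend Table 1 as follows.

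- **Footnote e:** *Week 1: 60 mg once daily for 24 weeks if 30 mg is tolerated and the participant does not have CKD-3; if CKD-3 is present and 30 mg is tolerated, 30 mg once daily for 24 weeks (see Section 6.1.1).*
- **Footnote f:** *Week 25: drug supply, taper or continuation as set out in Section 6.1.1.*
- **Revision date:** update it to that of the amendment.

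The new footnote e also restores the tolerability condition, and footnote f defers to the text, so neither creates a new conflict. The cost is an editorial amendment to two footnotes and a date. The design, sample size, analysis and dosing rules in Section 6.1.1 do not change.

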2 INTRODUCTION

2.1 STUDY RATIONALE

Significance

With our proposed work, we hope to address two important unanswered questions: (1) Does combination treatment consisting of duloxetine and web-based CBT optimize treatment outcomes? (2) Would adherence-focused guidance delivered by health care professional clinician using MI techniques enhance treatment effectiveness? Our proposed work is significant because we aim to optimize pain-related treatment outcomes at the primary care level where most patients with pain are managed. Importantly, the use of health care professional clinician providing adherence-focused guidance (as opposed to content-focused guidance) on the continued practice (or use) of pain coping skills increases the likelihood that our proposed intervention is scalable in the future. Effective, accessible and scalable psychoeducational treatments are needed to manage CMP in real world clinic settings ⁴.

Objectives

The **objective** of this UH3 application is to conduct a 24-week randomized clinical trial of primary care patients with CMP. In the UH3 trial, 280 participants will be randomized to one of three treatments: (1)

combination treatment [duloxetine + web-based CBT] with health care professional support, (2) combination treatment without health care professional support, and (3) duloxetine monotherapy.

Specific Aim 1. To compare combination treatment (with and without health care professional support) and duloxetine monotherapy in improving GPS (as measured by BPI pain severity and interference).

H1: Combination treatment with and without health care professional support is more effective than duloxetine monotherapy in improving GPS.

Specific Aim 2. To examine if health care professional support to increase participants' motivation on continued practice of pain coping skills will enhance treatment outcomes among those who receive combination treatment.

H2: Combination treatment with health care professional support is more effective than combination treatment without health care professional support in improving GPS.

2.2 BACKGROUND

Abnormal Endogenous Pain Modulation: Shared Biology among CMP Conditions

A major problem in designing new therapies to treat CMP is that the underlying mechanisms driving musculoskeletal pain are not fully understood ^{5,6}. In fact, physical findings in patients with CMP are poor predictors for self-reported pain severity and dysfunction ⁷. Moreover, the extent of tissue abnormalities appears to be poorly correlated with self-reported pain intensity ⁸. For example, minor radiographic abnormalities of the spine or knee may be painless in some individuals but may be associated with severe chronic pain in others ⁹. The poor correlation of patients' peripheral tissue abnormalities with chronic pain intensity has shifted research to focus on central pain processing abnormalities as the primary causal factors of chronic pain ¹⁰. Augmented central nervous system (CNS) processing of nociceptive signals and dysfunctional endogenous pain inhibition have been identified as characteristics of many musculoskeletal pain conditions ^{7,10-12} including low back pain, neck pain, temporomandibular disorder (TMD), osteoarthritis, and fibromyalgia ¹³⁻¹⁸.

Duloxetine: Efficacious in CMP Conditions

Augmented CNS processing of nociceptive signals and dysfunctional endogenous pain inhibition contribute to central sensitization. Central sensitization manifests as pain hypersensitivity, particularly tactile allodynia (painful response to a normally innocuous touch), pressure hyperalgesia, and enhanced temporal summation ¹⁹. In preclinical studies of pain, duloxetine, a selective serotonin norepinephrine reuptake inhibitor, reduces central sensitization ²⁰⁻²². In clinical studies, the efficacy of duloxetine is well documented in many of the musculoskeletal pain conditions including fibromyalgia ^{23,24}, osteoarthritis, and chronic low back pain ²⁵.

Psychological Factors in Chronic Pain

Two key factors that have important clinical implications for pain management are pain-related appraisals and beliefs (including catastrophizing), and pain coping ²⁶.

Pain-related appraisals and beliefs about pain can affect an individual's affective and behavioral response to pain^{27,28}. People are less able to adjust to pain when they believe that pain is a signal of damage, activity should be avoided when one has pain, pain leads to disability, pain is uncontrollable, and pain is a permanent condition ^{27,29}. For example, patients with low back pain believed that a wrong movement could have serious negative consequences for their back ². Moreover, this belief was

associated with reduced activity levels and increased disability. Among patients with fibromyalgia, positive outcomes were most closely related to: (1) an increased sense of control over pain, (2) a belief that one is not necessarily disabled by pain, and (3) a belief that pain is not necessarily a sign of damage³⁰.

One pain-related appraisal, catastrophizing (defined as an exaggerated negative orientation toward actual or anticipated pain experience and effects), has been an important therapeutic target in managing chronic pain³¹⁻³³.

Pain coping. Coping is the use of behavioral and cognitive techniques to manage demands perceived as stressful³⁴. Variations in pain coping are significantly related to pain, physical function and pain behavior³⁵⁻³⁷. Both active and passive coping dimensions are significantly related to chronic pain adjustment³⁸. In patients with osteoarthritis, greater self-control and increased rational thinking were associated with lower pain ratings and less self-reported physical disability³⁹. Among chronic pain patients, both poor coping skills and maladaptive pain related beliefs predicted physical disability²⁷. These findings suggest the importance of targeting specific pain-related beliefs and coping strategies for modification to reduce physical disability.

Cognitive Behavioral Therapy (CBT)

Modification of cognition (pain-related appraisals and beliefs) and behavior can positively or negatively affect the course of an individual's chronic pain condition. The goal of CBT is to aid the patient in re-conceptualizing his or her personal view of pain and role (from passive to a more proactive role) in the process of healing. CBT is effective in the management of low back pain, neck pain, temporomandibular joint pain, knee osteoarthritis, and fibromyalgia⁴⁰.

Scientific Premise

i. Optimizing Treatment Outcome: Combining Duloxetine and CBT

The bio-psychosocial model is particularly useful for understanding chronic painful conditions even when etiologies are vague^{41,42}. This model suggests that coping with illness involves a complex interaction of biological factors (central sensitization), psychological factors (mood and thoughts) and the social context (interpersonal relationships)⁴³. Along with drug management, a treatment approach based on the bio-psychosocial model involves addressing the psychosocial issues relevant to chronic pain. Unfortunately, only a few trials have tested medications plus non-pharmacologic treatments. In migraine headaches, the combination of beta blockers and behavioral migraine management was more effective than either therapy alone in reducing headache severity⁴⁴. In chronic tension headaches, tricyclic antidepressant plus stress management notably reduced the severity of headaches over 1 month, compared to either intervention alone⁴⁵. In non-cardiac chest pain, the combination of pain coping skills training and sertraline significantly reduced pain intensity and pain unpleasantness⁴⁶. In CMP, a collaborative care team approach that delivered multi-component treatment program (medication and pain self-management training) improved pain-related outcomes compared to usual care⁴⁷.

Preliminary Data: In our feasibility study⁴⁸, 58 patients with chronic widespread pain (fibromyalgia) were randomized to: (1) combination milnacipran (100 mg/day) + CBT (n=20), (2) milnacipran (100 mg/day) + education control (n=19), or (3) placebo medication + CBT (n=19). Participants received

either milnacipran (100 mg/day) or placebo. They also received 8 sessions of phone-delivered CBT or educational instructions. One of the primary endpoints was a composite responder rate; responders were defined as participants who reported a $\geq 30\%$ reduction from baseline in the weekly average pain severity, and ≥ 10 -point improvement from baseline in the SF-36 physical function score. We found a 41% composite responder rate for combination treatment versus 24% for milnacipran and 7% for CBT. We concluded that a therapeutic approach that combines CBT and milnacipran (*a medication closely related to duloxetine*) was feasible and acceptable⁴⁸. The observed effect sizes indicated that a full clinical trial was warranted.

While the reasons why medicine has not moved beyond the biomedical model are complex (e.g., inadequate economic incentives, continued focus on biomedical models in medical school education), the scarcity of comparative effectiveness studies to support the use of the bio-psychosocial model in CMP is another important factor.

ii. Web-based CBT to Improve Access

Despite the proven efficacy of traditional face-to-face CBT⁴⁹, access to care is one major limitation. Barriers to accessing face-to-face programs are numerous and include cost, stigma, and availability of psychologists that are trained in pain management. Consequently, the use of CBT in primary care where most patients with CMP are seen, is rare.

Web-delivered CBT is one innovative approach to increase access to pain management programs. Web-based programs use the same principles, content, and components as face-to-face programs but can be provided with varying levels of clinician support ranging from regular clinician contact to no clinician support at all.

Systematic reviews have reported *small but clinically significant* improvements in pain severity (effect size/ES= 0.33) and disability (ES= 0.39)^{50,51}.

iii. Importance of Maintaining and Enhancing Treatment Outcome of Web-based CBT

As in the in-person CBT protocol, participants in a web-based CBT program are typically asked to practice each new cognitive or behavioral pain coping skill after learning it. Fundamental to the long term effectiveness of CBT is the requirement that pain coping skills are applied or practiced on a regular basis. In a study of traditional CBT for chronic pain, pre- to post-treatment changes in pain control and catastrophizing mediated the effects of CBT on pain and activity interference⁵². In fibromyalgia, treatment outcomes were most closely related to 5 coping strategies or skills: decreased guarding, increased use of exercise, seeking support from others, activity pacing, and use of coping self-statements³⁰. Unfortunately, as with face-to-face CBT programs, maintenance of clinical improvements from web-based CBT has **not** been consistently observed⁵⁰ partly due to reduced use of cognitive and behavioral pain coping skills over time.

Rini C, Keefe F et al. evaluated the effectiveness of web-based CBT (+ physiotherapist-guided home exercise delivered through Skype) to 148 persons with chronic knee pain. Improvements in pain and function with the intervention were large at 3 months (immediate post-intervention) and were greater than those in the control group³. Benefits were apparent at follow-up, although between group differences were reduced. Further, 64% of the CBT practice exercises (i.e., relaxation, coping thoughts, pleasant imagery, distraction, problem solving, activity-rest cycling, pleasant activity

scheduling) were completed at 3 months with numbers decreasing during follow-up to 41%. Based on these findings, treatment strategies are needed to motivate continuous use or practice of pain coping skills to achieve long term success.

iv. MI to Enhance Benefits of Web-based CBT

MI is an effective counseling approach to elicit behavior change (e.g., from sedentary lifestyle to physically active lifestyle, from poor food choices to healthier food choices to achieve weight loss, etc.)⁵³⁻⁵⁷. In contrast to delivering simple advice, a MI-trained health care professional helps a patient discuss the pros and cons, and the barriers and solutions to behavior change; consequently, enhancing self-efficacy. Self-efficacy determines whether an individual attempts a given task, the degree of persistence when difficulty is encountered and ultimate success or failure of the behavior.

Preliminary Data: In our RCT study⁵⁸, 216 participants with fibromyalgia were randomized to MI to increase physical activity vs. education (attention) control. Over a 12-week period, participants received either **six** telephone-delivered MI or educational (attention control) instructions. Post intervention, MI was superior to control in increasing the number of weekly hours of self-report physical activity. At follow up, more MI participants than controls exhibited meaningful improvement in global severity. Additionally, participants in the MI group had a significantly greater improvement (i.e., walked longer distance) in the 6-minute walk test compared to controls.

Given our success on the use of telephone-delivered MI, it is reasonable to hypothesize that six sessions of telephone-delivered MI to increase participant's continued practice of pain coping skills will enhance treatment outcomes.

